#### 4.3.10 Exploratory Endpoints

##### 4.3.10.1 PK Analysis

The PK analysis of apaglutide is described in an external PK Analysis Plan (PK/PD Plan 2023).

##### 4.3.10.2 Quality of life and changes in subject-reported outcomes from baseline

##### **EQ-5D-5L**

For each of the 5 dimensions based on the descriptive system of the EuroQol5 dimensions-5 levels (EQ-5D-5L) questionnaire, the number and percentage of subjects for all categories (the 5 levels of reported problems and question not completed) and with missing data will be summarized by apaglutide dose levels and in total.

Descriptive statistics will be provided by apaglutide dose levels and in total for the EuroQol Visual Analog Scale (EQ VAS) score and changes in EQ VAS score from baseline by assessment.

##### **FACT-BMT**

Global and subscale scores will be derived from responses to the Functional Assessment of Cancer Therapy – Bone Marrow Transplantation [FACT-BMT] questionnaire.

For each of the 5 FACT-BMT subscales (physical well-being, social/family well-being, emotional well-being, functional well-being, and additional concerns – for which BMTS subscale is used-, the subscale score at a given assessment can be calculated according to FACT-BM Scoring Guidelines, Version 4 (Appendix C). For each subscale, a higher score represents a better quality of life (QoL).

The FACT-BMT total score is defined as the sum of the subscale score of all 5 FACT BMT subscales.

Descriptive statistics will be provided by apaglutide dose levels and in total for FACT-BMT global and subscale scores and changes in scores from baseline by assessment and by apaglutide dose levels and in total.

##### 4.3.10.3 Global assessment questionnaires

The frequencies and percentages within each of the response categories will be tabulated by visit by apaglutide dose levels and in total only, for the following questionnaires:

- Physician Global Assessment of Disease, five-point unipolar verbal scale of the overall severity of the subject's GVHD assessed by the patient's physician:

- 0, "No sign of disease"; 1, "Mild"; 2, "Moderate"; 3, "Severe"; 4, "Extremely severe".
- Patient Global Assessment of Severity, five-point unipolar verbal scale of severity of GVHD symptoms overall assessed by the subject:
  - 0, "Absent"; 1, "Mild"; 2, "Moderate"; 3, "Severe"; 4, "Extremely Severe"
- Patient Global Assessment of Change, five-point verbal bipolar scale of change in GHVH symptoms overall since the start of the trial medication, assessed by the subject:
  - -2, "A lot worse"; -1, "A little bit worse"; 0, "No change"; +1, "A little bit improved"; +2, "A lot improved"

*4.3.10.4 Body weight and parenteral support (volume and caloric content) at Days 14, 28, 56, 91, 119, 147 and 182 compared with baseline*

Descriptive statistics will be provided by apraglutide dose levels and in total for body weight and parenteral support. Changes from baseline to each scheduled visit, as well as the minimum, maximum, and last post-baseline values will be presented.

*4.3.10.5 Individual Need for blood transfusion from baseline up to Day 91*

The individual need for blood transfusions from baseline up to Day 91 is derived as the sum of the bags transfused during all transfusion procedures which took place between Day 1 and Day 91. Descriptive statistics will be provided by apraglutide dose levels and in total for the individual need for blood transfusions.

*4.3.10.6 Biomarker expression*

The following biomarker expression, clinical chemistry parameters, and lower GI histology (when available) related to GI-aGVHD, GI regeneration, and GI barrier function will be assessed at baseline and at times indicated in the schedule of assessments:

- Citrulline (measure of intestinal repair and regeneration) in plasma
- Regenerating islet-derived protein 3 alpha (REG3 $\alpha$ ) in serum
- Suppression of tumorigenicity 2 (ST2) in serum
- MAGIC algorithm probability (MAP) score, calculated according to the following formula:

$$\log[-\log(1 - \text{MAP})] = -11.263 + 1.844(\log_{10}\text{ST2}) + 0.577(\log_{10}\text{REG3}\alpha).$$

- Angiopoetin-1 and -2 in serum
- Soluble thrombomodulin (sTM) in serum
- Vascular endothelial growth factor (VEGF) in serum
- Albumin in serum
- Bilirubin in serum
- Presence of intestinal cell lines (L-cells, Paneth cells, intestinal stem cells) and status of mucosal architecture (crypts, villi) from histology slides of lower GI biopsies before apaglutide treatment and at the Day 56 visit (when biopsy data are available)
- Calprotectin in stool
- Microbial constitution of the stool microbiome

The biomarker expression data at each scheduled time point and changes from the baseline will be summarized using descriptive statistics by apaglutide dose levels and in total based on the SAS, only for subjects with at least one evaluable baseline sample and at least one evaluable post-baseline sample. Biomarker data may also be explored graphically (e.g., line plot of mean values over time) as needed.

Gut biopsy and Microbial constitution of the stool microbiome analyses will not be performed for the Primary analysis.

#### *4.3.10.7 Hospitalization up to Week 26*

The initial hospitalization is defined as the hospitalization for which Day 1 is comprised between date of admission and date of discharge.

The initial time to discharge from hospital is computed as time of discharge of the initial hospitalization - date of admission of the initial hospitalization + 1 Day.

The time to discharge from hospital up to Week 26 is defined as the sum of the time to discharge from any hospitalization which occurred between Day 1 and Day 182. The following rules will be applied to derive the individual time to discharge from a hospitalization:

- If a hospitalization started before Day1, the date of admission will be set to Day 1
- If a hospitalization ends after Day 182, or if end date is missing, the date of discharge will be set to Day 182
- The time to discharge from a hospitalization is then derived as  
time of discharge - date of admission + 1 Day

The number of readmission up to Week 26 is defined as the number of hospitalization, different from the initial hospitalization, which occurred between Day 1 and Day 182.

The duration of readmission up to Week 26 is defined as the sum of the time to discharge from any hospitalization which occurred between Day 1 and Day 182, except from the initial hospitalization.

The time to discharge from hospital up to Week 26, the number of readmissions up to Week 26 and the duration of readmission up to Week 26 following hospitalization data from Day 1 to Day 182 will be summarized descriptively by apaglutide dose levels and in total.

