### 3.3 Exploratory endpoints

- Pharmacokinetics of apaglutide assessed with a population PK (pharmacokinetic) approach. Absorption rate constant (ka), apparent clearance (CL/F), and apparent volume of distribution (Vz/F) with their intra- and inter-individual variability derived using a nonlinear mixed effects modeling approach, from sparse samples.
- Quality of life and changes in subject-reported outcomes from baseline (EuroQol 5 dimensions-5 levels [EQ-5D-5L], Functional Assessment of Cancer Therapy – Bone Marrow Transplantation [FACT BMT]).
- Global assessment questionnaires (Physician Global Assessment of Disease, Patient Global Assessment of Severity, and Patient Global Assessment of Change).
- Body weight and parenteral support (volume and caloric content) at Days 14, 28, 56, 91, 119, 147, and 182 compared with baseline.
- Individual need for blood transfusions (cumulative bags per subject) assessed from baseline to Day 91 [Only for Primary Analysis].
- Biomarker expression, clinical chemistry parameters, and lower GI histology (when available) related to GI-aGVHD, GI regeneration, and GI barrier function as assessed at baseline and at times indicated in the schedule of assessments:
  - Citrulline (measure of intestinal repair and regeneration) in serum
  - Regenerating islet-derived protein 3 alpha (REG3 $\alpha$ ) in serum
  - Suppression of tumorigenicity 2 (ST2) in serum
  - MAGIC algorithm probability (MAP) score consisting of REG3 $\alpha$  and ST2
  - Angiopoietin-1 and -2 in serum
  - Soluble thrombomodulin (sTM) in serum
  - Vascular endothelial growth factor (VEGF) in serum

- Albumin in serum
- Bilirubin in serum
- Presence of intestinal cell lines (L-cells, Paneth cells, intestinal stem cells) and status of mucosal architecture (crypts, villi) from histology slides of lower GI biopsies before apraglutide treatment and at the Day 56 visit (when biopsy data are available)
- Calprotectin in stool
- Microbial constitution of the stool microbiome
- Time to discharge from hospital, number of readmissions to an inpatient setting and duration of readmissions up to Week 26

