#### 4.1.2 *Handling of Dropouts and Missing Data*

Unless specified otherwise, missing data values will be recorded as missing and will not be imputed for the statistical analysis. Only observed data values will be used for the reporting of descriptive statistics.

Subjects with missing data such that the response, for instance the Day 56 lower GI response, cannot be determined will be included in the analysis as non-responders, consistent with intent-to-treat principle. The details for handling missing data and intercurrent events are specified in the estimand description in Section 4.3.9.2.

Censoring for time-to-event endpoint will be described for each endpoint separately.

In cases of missing or incomplete dates (e.g. AE and concomitant medications), the missing component(s) will be assumed as the most conservative value possible, taking the worst-case approach. Thus, an adverse event will be considered a treatment emergent adverse event (TEAE) unless the recorded dates conclusively prove otherwise. For example, if the start date of an AE is missing and the stop date either falls after the first dose of apraglutide or missing, then the AE will be considered a TEAE. When partial dates are present in the data, both a partial start date and/or a partial stop date will be evaluated to determine whether it can be conclusively established that the AE started prior to the start of apraglutide or stopped prior to the start of apraglutide. If the above cannot be conclusively established based on partial and/or present dates, then the AE will be considered TEAE.

For classification of prior and concomitant medications, the same conservative convention described above will be applied for handing missing or partial medication dates, and medications will be considered concomitant if it cannot be conclusively established whether or not they were taken at any point after the start of apraglutide.

If “Relationship to trial medication” field from the original case report forms (eCRFs) for an AE is missing, it will be imputed as “Definitely Related”.

In case of missing normal ranges for laboratory results, the normal ranges will be imputed using literature references (such as Merck, 2021) in the corresponding ADaM dataset for analysis purpose.

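### The hospital-stay variable has no rule for death or data cut-off, so a Day 20 in-hospital death scores 20 or 182 days depending on whether an end date is entered

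*SAP*

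**What the plan says.** SAP 3.3 lists the exploratory endpoint as "Time to discharge from hospital, number of readmissions to an inpatient setting and duration of readmissions up to Week 26". It carries no restriction to one analysis step, so under SAP section 1 it is produced at both the Primary Analysis and the EOT analysis.

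SAP 4.3.10.7 gives the derivation. The Week 26 time to discharge "is defined as the sum of the time to discharge from any hospitalization which occurred between Day 1 and Day 182". Each stay is computed as "time of discharge - date of admission + 1 Day", with two date rules:

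- Start: "If a hospitalization started before Day1, the date of admission will be set to Day 1".
- End: "If a hospitalization ends after Day 182, or if end date is missing, the date of discharge will be set to Day 182".

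Duration of readmissions is the same sum without the initial stay. The three Week 26 variables, "following hospitalization data from Day 1 to Day 182 will be summarized descriptively by apaglutide dose levels and in total". The section also defines the length of the initial stay by itself, but does not name it among the variables to be summarized. Death is not mentioned anywhere in the section.

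No other section fills the gap:

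- SAP 4.1.2 says "Censoring for time-to-event endpoint will be described for each endpoint separately"; 4.3.10.7 describes none.
- SAP 4.3.9.2 handles death (ICE1) for the MAGIC response estimands only.
- Protocol 5.5 has discharge dates, readmissions and stays recorded, but does not say what is entered when a stay ends in death.

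By contrast, SAP 4.3.6.2 stops the imputation of steroid and ruxolitinib doses at Day 91, trial discontinuation or death.

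**The concern.** A stay can close in several ways: live discharge, death, loss of contact, data cut-off, or still in hospital at Day 182. The derivation treats any recorded end date as a discharge and any missing one as a stay that lasted to Day 182. It therefore does not separate death from discharge, and it can count days that the subject did not live or that nobody has yet observed.

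Death is not a rare complication here. Protocol 1.1 cites 6-month survival of 51.0% in the single-arm ruxolitinib trial, and exclusion criterion 9 removes only subjects expected to survive less than 2 weeks. What is at stake is whether the tabulated hospital days, by dose and in total, can be read for the health-economics objective in Protocol 1.5.1.3. If the end-date convention for deaths is unstated or varies between sites, a reader cannot tell what the number measures.

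**Working it through.** The documents give no figure for this endpoint, so there is nothing to reproduce. The check applies the SAP rules to simple cases.

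**Rule.** Start = max(admission, Day 1). End = Day 182 if missing or later, otherwise the recorded date. Days = end − start + 1.

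**Single subjects, admitted before Day 1**

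| Case | End date recorded | Score (days) |
|---|---|---|
| Discharged alive on Day 20 | Day 20 | 20 − 1 + 1 = 20 |
| Died in hospital on Day 20 | Day 20 | 20 − 1 + 1 = 20 |
| Died in hospital on Day 20 | blank | 182 − 1 + 1 = 182, of which 182 − 20 = 162 after death |
| Alive in hospital at cut-off on Day 95 | blank | 182, of which 182 − 95 = 87 unobserved |

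The last row can arise because SAP section 1 allows the Primary Analysis once subjects have reached Day 91 and removes data after the cut-off. That the cut leaves such a stay without an end date is an inference; the derivation does not say.

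**An arm of 15** (the size per dose in Protocol 7.4). Assume that survivors are discharged on Day 40 and that k subjects die in hospital on Day 10. The mean is (10k + 40(15 − k))/15 if the death date is entered and (182k + 40(15 − k))/15 if the field is blank.

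| Deaths k | Mean, death date entered | Mean, blank |
|---|---|---|
| 0 | 40.0 | 40.0 |
| 2 | 36.0 | 58.9 |
| 4 | 32.0 | 77.9 |
| 6 | 28.0 | 96.8 |

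Identical outcomes move the mean down under one convention and up under the other. For scale, at 51% survival about 15 × 0.49 = 7.35 subjects per arm would die within 6 months, in or out of hospital.

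**Simulation.** One stay per subject, exponential times, an assumed median of 30 days to live discharge held fixed, and 6-month survival of 90%, 51% and 30%. Mean days fall from 42.2 to 37.5 to 34.0 if death ends the stay, and rise from 45.5 to 57.2 to 66.5 if the field is blank. With a median of 60 days they fall from 73.9 to 62.0 to 53.5, or rise from 79.0 to 91.0 to 100.1.

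**The alternative summary.** In the same simulation, the cumulative incidence of live discharge by Day 182, with in-hospital death as a competing event, is 96.3%, 85.7% and 77.7% (median 30 days) or 84.8%, 71.1% and 61.4% (median 60 days). It falls as mortality rises, and it does not use an imputed end date for deaths.

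**The case against.** **Exploratory and descriptive.** SAP section 6 drops the dose-effect endpoint because no formal comparison will be made (item 12), and no comparison with external data was planned for the Primary Analysis (item 7). This stands and limits the importance of the point. A reader might infer that any comparison on this variable would be uninterpretable. The documents do not support that: the comparisons it would damage are not planned, and the damage depends on an unknown convention.

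**Higher mortality need not look favourable.** A reader might infer from the first column of the arm table that the sickest group looks best. That needs the death date to be entered as the end of stay, and a discharge rate that does not slow as mortality rises. Neither is in the documents. Take exponential times and no readmissions, with h the sum of the discharge and death hazards, so that mean stay is (1 − exp(−182h))/h. At 6-month mortality of 10%, 30% and 50%, a fixed mean of 60 days to discharge gives 55.5, 51.9 and 47.7 days. If that mean lengthens to 60, 70 and 80 days, the results are 55.5, 58.4 and 58.2 days and the ordering is gone. Both sets of inputs are assumptions. This objection stands.

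**Resource use.** For health economics, inpatient days ending at death are the quantity consumed, and mortality is reported elsewhere. This supports keeping the sum. It does not support calling it time to discharge or counting days after death.

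**Other documents may settle it.** Protocol 10.3 provides for queries on omissions, and SAP sections 1 and 5 refer to separate dataset and programming specifications that are not available here. Blank end dates may prove rare. But the SAP rule as written gives Day 182 whenever one occurs, and what a death means for an endpoint belongs in the SAP.

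**Conclusion.** The point holds in a limited form. The end-date rule in SAP 4.3.10.7 yields wrong values in cases that can be expected in this trial: up to 162 days after death for a Day 20 in-hospital death with a blank end date, and 87 unobserved days for a survivor in hospital at a Day 95 cut-off. Where the death date is entered, the death is indistinguishable from a live discharge.

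The single-subject scores follow directly from the SAP rules. The arm means and the simulation rest on assumed discharge and death times and show scale only. How often end dates are blank, and what sites enter at death, cannot be known from the documents, so the direction of the net distortion is not fixed. Because the endpoint is exploratory and summarized descriptively, this is a desirable correction that does not affect the trial's main conclusions.

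**What to change.** In SAP 4.3.10.7:

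1. End every stay at the earliest of discharge, death, last contact, data cut-off or Day 182, and never impute past death or cut-off. State how each stay ended.
2. Relabel the sum as total hospital days to Day 182, and show how many subjects were followed to Day 182, died before it, or were still under observation at the cut-off.
3. Report time to first live discharge for subjects in hospital on Day 1 as a cumulative incidence, with in-hospital death as a competing event and open stays censored at last contact or cut-off. Step 1 alone would still score a Day 20 death like a Day 20 discharge. Protocol 7.8.2 already plans cumulative incidence for secondary time-to-event endpoints with competing risks.
4. Optionally, add days alive and out of hospital to Day 182 for subjects with full follow-up, counting days after death as zero.

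The cost is a few lines of SAP text and a small amount of extra derivation. Hospital-stay dates and deaths are already collected, so no new data are needed.

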## 5 PROGRAMMING SPECIFICATIONS

Detailed Programming Specifications for the figures, listings and tables that will be generated for the Primary and EOT analyses will be provided in a separate document.

## 6 CHANGES FROM PROTOCOL-SPECIFIED STATISTICAL ANALYSES

1. Analysis Day will not include Day 0, per CDISC compliance, whereas protocol considers Day 0. The distinction between visits and analysis days is detailed in Section 4.1.1.
2. Treatment description is broken down into main treatment (W0-W7) and extension treatment (W8-W13), for analysis purpose.
3. Sample size determination explicitly refers to durable overall response on the Lower GI MAGIC score.
4. Wording of the definition of Additional systemic therapies in Appendix A has been added for completeness.
5. The AE Grading for on-sites reactions was contradictory in the protocol and is clarified in Section 4.3.8.1
6. The SAS1 and SAS2 analysis population were merged in a single analysis population, as the analysis output formatting can provide equivalent information.
7. Due to the absence of adequate historical control, the comparison to external data on BAT was not planned for the Primary Analysis.
8. Brookmeyer-Crowley confidence interval levels are set to 95% (instead of 90% in protocol) for consistency of levels between confidence intervals.
9. Duration of response from Day 28 and Day 56 on the total MAGIC score are analyzed regardless of follow-up duration, with right-censoring for subjects who did not reach the 182 days of follow-up at data cut-off.

10. The incidence of infections and sepsis from baseline are analyzed up to Day 91 but also up to the end of the trial.
11. Physical examination was added in the list of safety endpoints as the protocol states that physical examination will be analyzed as safety endpoint.
12. The following endpoint listed in the protocol was removed from the list of endpoints as no formal comparison will be performed: Effect of the two dose groups on safety/tolerability and efficacy

## APPENDIX A: DEFINITIONS OF TERMS

The following definitions will apply in this trial:

Term	Definition
Graft failure	
Primary graft failure:
 
Absolute neutrophil count <math><0.5 \times 10^9/L</math> by Day 28 Hemoglobin <math><80 \text{ g/L}</math> and platelets <math><20 \times 10^9/L</math> Reduced intensity conditioning: Confirmation of donor cell origin is required Cord blood transplant: Up to Day +42
 
Secondary graft failure:
 
Absolute neutrophil count <math><0.5 \times 10^9/L</math> after initial engraftment not related to relapse, infection, or drug toxicity Reduced intensity conditioning: Loss of donor hematopoiesis to <math><5\%</math>

Failure-free survival	The time from the date of randomization/Day 0 to the date of hematologic malignancy relapse/progression, non-relapse mortality, or addition of new systemic acute graft versus host disease (aGVHD) treatment
Non-relapse mortality	The time from date of randomization/Day 0 to date of death not preceded by hematologic malignancy relapse/progression
Overall survival	The time from the date of randomization/Day 0 to the date of death due to any cause
Malignancy relapse/progression	The time from date of randomization/Day 0 to hematologic malignancy relapse/progression
Complete response	A score of 0 for the aGVHD grading in all evaluable organs that indicates complete resolution of all signs and symptoms of aGVHD in all evaluable organs without administration of additional systemic therapies for any earlier progression, mixed response or non-response of aGVHD


“Additional systemic therapy” definition for the complete and partial response definition
	
Any GVHD systemic therapy being started after apaglutide initiation to achieve GVHD control, i.e. any medication or procedure marked as Reason for medication = “aGVHD treatment” and “Is this an additional, new systemic therapy for an earlier progression, mixed response or non-response of aGVHD?” = Yes in the CM or PR page of the eCRF.
 
Note:
 
 
- Increases or addition of a new systemic steroid will not be counted as new or additional GVHD therapy.
 
Budesonide and beclametasone not to be considered as new GVHD therapy
 
- Change in dose of CNIs will not be considered as additional GVHD therapy if already given prior to apaglutide
 
 
New CNIs after apaglutide initiation should be considered as a new systemic therapy, if marked as “aGVHD treatment” and “Is this an additional, new systemic therapy for an earlier progression, mixed response or non-response of aGVHD?”; these will not be considered as new therapy if marked as “prophylaxis for a drug side effect”.

Complete lower gastrointestinal (GI)-aGVHD response
	
The resolution of all lower GI-aGVHD signs and symptoms (score of 0 for aGVHD grading) of GVHD without administration of additional systemic therapies for any earlier progression, or non-response of lower GI-aGVHD.

Partial response
	
An improvement of one stage in one or more organs involved with aGVHD signs or symptoms without progression in other organs or sites without administration of additional systemic therapies for an earlier progression, mixed response, or non-response of aGVHD

Partial lower GI-aGVHD response
	
An improvement of one stage in the signs and symptoms of lower GI-aGVHD without administration of additional systemic therapies for any earlier progression or non-response of lower GI-aGVHD.

Lack of response	Defined as stable disease, mixed response, or progression
Stable disease	An absence of improvement in all organs involved by aGVHD, without worsening in all involved organs or development of signs or symptoms of aGVHD in a new organ
Stable disease (lower GI-aGVHD)	An absence of improvement or absence of worsening in lower GI-aGVHD
Mixed response	An improvement of at least 1 stage in the severity of aGVHD in one organ accompanied by progression in another organ or development of signs or symptoms of aGVHD in a new organ
Progression	Worsening in one or more organs by one or more stages without improvement in any other involved organ
Lower GI-aGVHD progression	Worsening in lower GI-aGVHD per MAGIC lower GI-score compared with baseline
Lower GI-aGVHD flare	
Any increase in signs or symptoms of lower GI-aGVHD that is sustained for >24 hours after an initial response (CR or PR) and requires re-escalation of immunosuppressive therapy (e.g., corticosteroid, calcineurin inhibitors and/or ruxolitinib dosing).
 
While all aGVHD flares will be captured during the trial whether occurring during steroid, CNI, BAT or ruxolitinib taper, only flares that fulfil either one the following criteria will be considered a failure of treatment:
 
 
1. Addition of new systemic therapy for lower GI-aGVHD due to inability to taper corticosteroids below methylprednisolone (MP) 0.5 mg/kg/day (or equivalent <0.6 mg/kg/day of prednisone) for a minimum 7 days
 
 
OR
 
 
2. Addition of new systemic therapy for lower GI-aGVHD due to re-escalation of corticosteroids to MP >2 mg/kg/day (or equivalent >2.5 mg/kg/day of prednisone)
 

Best overall response	The best response recorded from the start of the treatment up to Day 91 or the start of additional systemic therapy for GI-aGVHD

Best overall lower GI-aGVHD response	The best response of Lower GI-aGVHD response recorded from the start of the treatment up to Day 91 or the start of additional systemic therapy for GI-aGVHD
--------------------------------------	---

